The intervention will use commercially available RS-2 (Hi-Maize) that will be prepared into common bakery items, such as muffins, scones, as well as beverages such as smoothies. Control products will use the same recipe but will be prepared with regular corn starch. The RS will be Hi-Maize, a corn starch made solely from hi-amylose maize. This product is commercially available from, among others, King Arthur Flour, Honeyville and Amazon. It has been used in many published studies⁸⁵⁻⁹³ as well as at least 20 studies currently listed in ClinicalTrials.gov. Dose range has been from 15g/day to 47g/day and study duration from 1 to 8 weeks. Some people may experience flatulence and perhaps some bloating due to the higher fiber content added to their diet, therefore we will have participants do a stepwise escalation that will allow for better adaptation to the target dose of 30g. RS per day. In the first two weeks participants will consume one study food with 15 g RS per day and starting in the third week participants will consume two study foods for a total of 30g RS per day for 6 weeks. Participants will be provided with a variety of options to allow for variety. No other dietary changes will be required. Participants may consume their usual diet and participate in their usual activity throughout the study. All products will be produced at the Human Nutrition Lab in the Fred Hutch Prevention Center. See Figure 2.

Systemic inflammation will be measured as serum C-reactive protein (CRP)/albumin ratio and adiponectin. Insulin resistance will be assessed using the homeostasis model of assessment-insulin resistance (HOMA-IR). Gut microbial community structure (16S rRNA sequencing), and gut metabolites will be compared between intervention and control groups for generation of hypotheses for protective prebiotic effects on gut microbial taxa.

In order to determine whether an RS dietary intervention can potentially affect gastrointestinal tumorigenesis in high-risk individuals, participant fecal microbiota sampled will be transplanted into colorectal tumor-prone mice ([name], UW IACUC protocol # 4418_01).

[figure not shown]
Primary Aim: To determine the feasibility of an 8-week dietary intervention testing foods made with resistant starch compared to foods made with corn starch in patients who have completed treatment for stage I-III colorectal cancer. Feasibility will be assessed based on trial accrual, intervention adherence, and trial retention.

Secondary Aims:

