Study staff provides the participant with study supplies for the next six weeks. These supplies consist of: (1) instructions for weekly or every other week receipt of study foods from the Fred Hutch Human Nutrition Lab (foods will be mailed, couriered, or the participant may opt to pick up their foods in person); (2) the Daily Study Food Consumption and Symptoms Log with instructions to complete daily for days 14 through end of study; and (3) another stool collection kit with instructions for the 3rd intervention visit.

Study staff also reminds the participant that staff will call the participant every other week through end of study. The purpose of these calls is to check in, remind the participant to eat the study foods daily at the appropriate dosage levels, and provide the participant an opportunity to ask questions.

Randomized, Controlled Trial of Resistant Starch in Stage I-III Colorectal Cancer Survivors Pilot Study: The Fiber for Health After Cancer Study

These calls also will ascertain what specific study food products the participant would like to order from the research kitchen for his/her next batch of study foods, and how he/she would like to receive them (delivery method). (See Adherence Call Script, Appendix 15).

4.e. INTERVENTION VISIT 3 - END OF INTERVENTION – Week 8 – Day 56

Participants return to the Prevention Center on Day 56 for their Week-8 and final visit. At this visit, the participant will bring in a final stool sample, the completed Study Questionnaire (Week-8 Follow Up time point), and the Daily Study Food Consumption and Symptoms Log completed for days 14 through end of study. If participant is unable to come to the Prevention Center, the stool sample and questionnaires can be returned by mail.

Summary of Intervention Visit 3 Activities

Participants turn in their completed Week-8 follow-up questionnaires

1. Study Questionnaire (Week-8 Follow Up)
2. Daily Study Food Consumption and Symptoms Log (for Weeks 3-8)

Week-8 follow-up biological samples are collected:

3. Stool
4. Blood (fasting) -10 cc

Study staff provides the participant with End of Study Thank You Letter and \$50 Visa Gift Card.

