Alternatively, if necessary for example during the COVID-19 pandemic, this visit may be conducted telephonically (using script per Appendix 20). Should this visit need to occur by telephone, the end-of-study fasting blood draw will not be collected. The participant will be instructed to collect the stool sample using the kit provided for the end-of-study collection.

The participant will be sent a pre-paid, same day courier return mailing label and box to return the frozen stool sample and end-of-study questionnaires. Depending on accessibility of the participant to his/her neighborhood courier office, the participant can either take the shipment box to the courier office, or study staff can arrange for pick-up service by the courier from the participant's home. In the event of a 'shelter in place' mandate, the latter option will be used. In the event that the courier service is not operating, the participant will be instructed to keep the study materials at home, and the stool sample in his/her home freezer, until the courier service is again operational.

The end of study thank you letter and \$50 thank you payment will be mailed to the participant upon receipt of the end of study stool sample and questionnaires.

4.f. MANAGING POTENTIAL DELAYS OR DISRUPTIONS TO THE STUDY CALENDAR

This component of the study protocol is added as a result of the Fred Hutch laboratory ramp down in response to the coronavirus pandemic.

In response to the pandemic, or any other unanticipated natural disaster, it is possible that the start of intervention may need to be delayed. For other participants who may have already started the intervention, the intervention may need to be stopped early. Here we describe how each of these scenarios will be handled.

Should the start of the intervention need to be delayed:

Randomized, Controlled Trial of Resistant Starch in Stage I-III Colorectal Cancer Survivors Pilot Study: The Fiber for Health After Cancer Study

In the event that a delay in the start of the intervention be necessary, the consented participant will be called and/or emailed (using script per Appendix 21). The reason for the need to delay the start of the intervention and the remainder of the study calendar will be explained to the participant. This call/email will involve either scheduling the new study intervention dates (if possible) or scheduling a date to check in with the participant again by phone to provide study status.

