If at any time after dose reducing to 15g/day during Week 3-8 the participant experiences new or continuing ≥ grade 3 AE(s) that are possibly, probably, or definitely related to the study dietary intervention	
Stop the dietary intervention and continue as follows as soon as possible (within one week) after stopping the study food product:
 
➤ Collect the end of study stool sample and study questionnaire (originally planned for Week 8). (Participant may send stool sample and Questionnaire by mail or deliver in person to the Prevention Center).➤ Collect the end of study fasting blood draw (originally planned for Week 8), at the Prevention Center➤ Provide EOS Thank You Letter and Gift Card.

Randomized, Controlled Trial of Resistant Starch in Stage I-III Colorectal Cancer Survivors Pilot Study: The Fiber for Health After Cancer Study

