8. DATA ANALYSIS PLAN

Feasibility Endpoints.

Feasibility of the study design and intervention will be assessed based on the following three criteria:

1. Accrual. The accrual rate will be estimated with a target accrual rate of full enrollment within 12 months after study activation.
2. Adherence. Adherence to the intervention will be defined as consuming 75% or more of study foods on $\geq 75\%$ of days from baseline to 8 weeks.

Randomized, Controlled Trial of Resistant Starch in Stage I-III Colorectal Cancer Survivors Pilot Study: The Fiber for Health After Cancer Study

3. **Retention.** Target retention is defined as ≥80% of enrolled participants providing blood and stool samples at 8 weeks.

Secondary Endpoints.

Secondary endpoint analyses will be considered exploratory and will be used to provide effect size estimates to be used in a future trial.

1. Assess variability in biomarkers of insulin resistance and inflammation will be assessed using descriptive statistics.
2. Assess variability in gut microbial communities from human stool samples collected during the study by changes in alpha diversity, global microbial community (beta diversity), and genera in response to the intervention. We will use multivariate and univariate approaches to assess significant changes in the microbiome in response to the intervention.
3. Fecal microbiota from “resistant starch responders” (i.e., individuals with significant resulting elevations in fecal short-chain fatty acids concentrations) will be selected as input samples in gnotobiotic mouse studies, in which mice will be fed diets with or without resistant starch in order to characterize effects on tumorigenesis in an otherwise controlled environment. We predict that the chemoprotective effect of this diet intervention will be dependent upon gut microbial metabolism.

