Plan for annual reporting: A summary of the investigation including all adverse events and how they were handled, enrollment, drop-outs and reason for discontinuation and any protocol modifications will be provided to the IRB on an annual basis.

Annual Reports will contain:

- a. The number of adverse events and an explanation of how each event was handled
- b. The number of complaints and how each complaint was handled
- c. The number of subject withdrawals and an explanation of why the subject withdrew or was withdrawn
- d. The number of protocol deviations and how each was handled

Any questions of food safety will be immediately reviewed with the HNL manager. The occurrence of any serious and unexpected event may prompt changes in study protocol. Any such change will be approved by the IRB before implementation.

Randomized, Controlled Trial of Resistant Starch in Stage I-III Colorectal Cancer Survivors Pilot Study: The Fiber for Health After Cancer Study

Monitoring for data integrity and safety will be the responsibility of the investigators and the CRS Monitoring program.

Investigators will include the following in routine monitoring review: A) Validity and integrity of data: Data are checked for missing, unusual, or impossible records when they are entered into the study's computer database. The investigators may consider modifications to the data collection protocol with permission from IRB if they deem the change(s) is necessary to ensure the validity and integrity of data collected. B) Enrollment rate relative to expectation: Early lags in recruitment will be rectified with increased recruitment efforts so that recruitment will be completed on time. The investigators will monitor this closely to ensure full enrollment of appropriate participants. C) Retention of participants and adherence to protocol: The investigators will monitor retention and adherence to study protocol. Adherence to the study diet will be monitored via the Daily Record that participants fill out and the uneaten foods they return.

In addition, a CRS monitoring visit will occur approximately 12 months after the first participant is enrolled, and will comprise, at a minimum, consent document review and eligibility review for 10% or 3 participants enrolled. Additional monitoring may occur if so recommended by the CRS Monitoring program.

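### The retention endpoint requires week-8 blood, so anyone finishing by the permitted telephone visit is scored as a dropout; if such finishers occur, trial retention is understated by their share

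*Combined protocol and SAP*

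**What the plan says.** The only definition of retention is in Section 8, item 3: "Target retention is defined as ≥80% of enrolled participants providing blood and stool samples at 8 weeks". Retention is one of the three parts of the primary aim in Section 1: "Feasibility will be assessed based on trial accrual, intervention adherence, and trial retention".

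Section 4.e expects Visit 3 to take place in person but allows a telephone visit where necessary, with the pandemic as the example. For that form of the visit it states: "Should this visit need to occur by telephone, the end-of-study fasting blood draw will not be collected". Stool is still collected at home and returned by courier with the questionnaires. The thank-you letter and payment "will be mailed to the participant upon receipt of the end of study stool sample and questionnaires", so blood is not a condition.

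Section 4.e also offers a mail route: "If participant is unable to come to the Prevention Center, the stool sample and questionnaires can be returned by mail". It does not say what happens to the blood draw in that case. The Study Overview in Section 1 places the fasting draws at the Prevention Center, and no home or local draw is described anywhere.

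Section 8 contains no exception, second count or sensitivity analysis for participants who finish remotely.

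**The concern.** Two parts of the protocol work against each other. Section 4.e treats the telephone visit as a legitimate way to reach the end of the study. Section 8 makes it impossible for anyone who takes it to be counted as retained. The mode of the visit then decides the score, whether or not the participant stayed with the intervention.

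At stake is how a primary feasibility result is read. One percentage would pool people who left with people who ate the foods for eight weeks and returned everything asked of them. Someone planning a larger trial could conclude that survivors do not stay in an eight-week food intervention, when the real problem was access to the phlebotomy site.

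Section 9 does not close the gap. It provides that "enrollment, drop-outs and reason for discontinuation and any protocol modifications will be provided to the IRB on an annual basis", so the information needed to separate the two groups should exist. But a telephone finisher is not a drop-out in that report and is not retained under Section 8, and nothing reconciles the two counts.

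**Working it through.** **The stated figure.** The 80% is a chosen threshold. The documents give no sample size, expected dropout or power behind it, so there is nothing to reproduce. The check is whether the rule measures what it is named for, and by how much it could miss.

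**The rule applied to each way of reaching week 8**

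| Route | Stool | Blood | Score under Section 8, item 3 |
|---|---|---|---|
| In-person Visit 3 (4.e) | collected | collected | retained |
| Telephone Visit 3 (4.e) | by courier | not collected, stated | not retained |
| Mail return (4.e) | by mail | no route given; absence implied only | not retained, if blood is in fact missing |
| Withdrawal or loss | none | none | not retained |

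The second and fourth rows receive the same score.

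**Inputs**

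- Target 80%, denominator all enrolled: Section 8, item 3.
- r = share of enrolled participants completing week-8 follow-up by any permitted route: not in the documents; assumed 90% and 95%.
- f = share of enrolled participants who complete week-8 follow-up remotely and give no blood: not in the documents; shown from 0 to 20%.
- Assumption: every other finisher gives both samples.

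**Formulas.** Measured retention = r − f. Shortfall against trial retention = f. Ceiling, when r = 100%, = 1 − f. The figure falls below target once f > r − 0.80.

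| f | r = 95% | r = 90% |
|---|---|---|
| 0% | 95% | 90% |
| 5% | 90% | 85% |
| 10% | 85% | 80% |
| 15% | 80% | 75% |
| 20% | 75% | 70% |

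The break-even points are 0.95 − 0.80 = 15 percentage points and 0.90 − 0.80 = 10 percentage points.

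**Cross-check with a different parameter.** Let d be true dropout and t the remote share among completers. Measured retention is then (1 − d)(1 − t), and the largest t that still reaches 80% is 1 − 0.80/(1 − d). At d = 10% this is 11.1%, and 0.90 × 11.1% = 10% of enrolled. At d = 5% it is 15.8%, and 0.95 × 15.8% = 15% of enrolled. Both agree with the table.

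**In counts, with N assumed for illustration**

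- N = 20 needs 0.80 × 20 = 16. At r = 95%, 19 finish; a fourth remote finisher leaves 15/20 = 75.0%. At r = 90%, 18 finish; the third leaves 15/20.
- N = 40 needs 0.80 × 40 = 32. At r = 95%, 38 finish; a seventh remote finisher leaves 31/40 = 77.5%. At r = 90%, 36 finish; the fifth leaves 31/40.

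**Two related gaps in the same definition**

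- Section 6 brings some end-of-study samples forward after an adverse-event stop, and Section 4.f allows the institution to end a participant's intervention before week 8. Section 8 does not say how either group is scored. If early samples were counted as 8-week samples, the figure would move upward.
- Section 4.b omits baseline blood when Visit 1 is by telephone. A participant with a telephone Visit 1 and an in-person Visit 3 is retained under Section 8 but gives no baseline-to-week-8 biomarker change, which secondary aim 1 needs.

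**The case against.** The best defence is that the definition is explicit and deliberate. The human secondary aims depend on blood markers and stool microbiota, and the pilot is meant to inform a later trial. Counting only participants who supply both specimens is a legitimate and conservative choice, and a reader who sees the definition beside the figure knows what was counted. This stands in part: as specimen availability the figure is valid. It does not justify the name, because the primary aim speaks of trial retention. Nor does the figure fully serve the biomarker aim, since week-8 blood does not guarantee a baseline pair.

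It is also fair that the telephone visit is a contingency and attendance is the default, that N, r and f are all assumed, and that Section 9 already has drop-outs and reasons reported. These points limit the size of the problem without removing the conflict.

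Three stronger readings are tempting and not supported:

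- A reader might infer that the figure will be too low. It is too low only if someone finishes without blood, and the unstated scoring of early Section 6 samples could push the other way.
- A reader might infer that the mail route also excludes blood by rule. Section 4.e leaves this implied.
- A reader might take the completion payment as proof that telephone finishers are regarded as completers. That is weak evidence, because participants stopped early under Sections 4.f and 6 receive it too.

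**Conclusion.** The conflict is in the text and does not depend on any assumption: Section 8, item 3 scores a protocol-compliant telephone finisher the same as a dropout. Its numerical effect is conditional. If such participants occur, trial retention is understated by their share f of all enrolled, given that the remaining finishers supply both samples; if none occur, the effect is nil. Whether the 80% line is crossed depends on values the documents do not give.

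A reader might go further and say that the trial would fail its feasibility test. The documents do not support that, because they contain a target but no go/no-go rule. The harm is a feasibility percentage that can mislead, from a measure that is sound under a different name.

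**What to change.** Before analysis, amend Section 8, item 3 to report the following over all enrolled participants, with an exact 95% confidence interval for (a) and (b):

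- (a) *Trial retention*: week-8 follow-up completed by any route Section 4.e permits (in person, telephone or mail), whichever specimens were obtained. Apply the 80% retention target to this figure. Name the record that shows completion; the week-8 questionnaire is requested on every route and is not a specimen.
- (b) *Week-8 blood-and-stool availability*: the existing figure, unchanged apart from its label, also shown against 80%.
- The number of participants with paired baseline and week-8 blood, for secondary aim 1.

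Add a short table of participants not counted in (a) or (b), by reason: remote visit without blood; institutional stop under Section 4.f; adverse-event stop under Section 6, with early samples shown as their own category and not as 8-week samples; withdrawal or loss.

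The cost is a paragraph, one extra figure and a short table, from data the study already collects. The small downside is that (a) alone no longer guarantees a blood sample, so (a) and (b) must always be shown together.

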
1. To assess variability from baseline to 8 weeks in circulating markers of insulin resistance (glucose, insulin and HOMA-IR) and inflammation (CRP, albumin, adiponectin), by randomization arm.
2. To assess variability from baseline to 2 weeks and 8 weeks in gut microbial communities based on 16S rRNA gene sequencing, by randomization arm.
3. To explore whether resistant starch suppresses adenomas/carcinomas in human to mouse Fecal Microbiota Transplantation (FMT) studies.

Randomized, Controlled Trial of Resistant Starch in Stage I-III Colorectal Cancer Survivors Pilot Study: The Fiber for Health After Cancer Study

Figure 2 – Study Design. Note: The Stool Only protocol and companion Intervention Pilot have separate protocols and IRB submissions. [name], Co-PI, will receive human fecal samples for the gnotobiotic mouse experiments under IACUC approval (UW IACUC protocol # 4418_01).

Randomized, Controlled Trial of Resistant Starch in Stage I-III Colorectal Cancer Survivors Pilot Study: The Fiber for Health After Cancer Study

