We will work with each participant individually to plan how food items will be delivered to them during the course of the study. If a participant is willing and able to come to the Prevention Center once a week or once every 2 weeks, this gives us the opportunity to meet with them face to face and discuss any issues they may be having. If it is not practical for the participant to come to the Prevention Center to receive his/her study food items, we will arrange for delivery of the items via U.S. Mail, Federal Express, in person delivery by study staff, or courier. The HNL has done this procedure for other studies as well. The informed consent form will provide participants the opportunity to consent to their names and delivery addresses to be provided by study staff to the US Postal Service, Federal Express or courier service as needed.

Randomization into active or control group: Participants will be block randomized based on sex and 2 BMI categories. This will ensure that the two intervention arms have similar distributions of patients.

Active and control groups will be blinded, products will be labeled either A or B, and will be unblinded by the Human Nutrition Lab to investigators once study and data analysis has been completed.

Compliance measures: we will provide a calendar-driven, checklist-style daily log for participants to mark having eaten the study food items and, if not completely, how much. This log will also have a place for the participant to record any gastrointestinal issues they may be experiencing.

Interim compliance contacts: the research coordinator will contact the participant (via phone call once weekly through ramp up to 30g daily then every two weeks thereafter through end of study. (See Adherence Call Script, Appendix 15).

Randomized, Controlled Trial of Resistant Starch in Stage I-III Colorectal Cancer Survivors Pilot Study: The Fiber for Health After Cancer Study

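### Does the exploratory mouse transplant study need comparator donors, given that Section 8 names only responders and varies only the mouse diet?

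*Combined protocol and SAP*

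**What the plan says.** Section 8, Secondary Endpoints, item 3 sets the donor rule: "individuals with significant resulting elevations in fecal short-chain fatty acids concentrations) will be selected as input samples in gnotobiotic mouse studies". The experimental factor follows: "in which mice will be fed diets with or without resistant starch in order to characterize effects on tumorigenesis in an otherwise controlled environment". The item closes with an expectation: "We predict that the chemoprotective effect of this diet intervention will be dependent upon gut microbial metabolism". All secondary analyses carry the same status: "Secondary endpoint analyses will be considered exploratory and will be used to provide effect size estimates to be used in a future trial".

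Section 1 describes the same work twice. The Study Overview gives the reason for transplanting: "In order to determine whether an RS dietary intervention can potentially affect gastrointestinal tumorigenesis in high-risk individuals". Secondary Aim 3 reads: "To explore whether resistant starch suppresses adenomas/carcinomas in human to mouse Fecal Microbiota Transplantation (FMT) studies". Neither statement limits donors to responders. Section 10 (Stool) also sends the anaerobic samples for transplantation without naming an arm, a visit or a response group. The Figure 2 caption places the mouse work under separate oversight: the co-investigator "will receive human fecal samples for the gnotobiotic mouse experiments under IACUC approval".

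The text available names no baseline, control-arm, non-responder or untransplanted comparator for the mice. It gives no number of mice or donors and no variance.

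**The concern.** Dependence on microbial metabolism is an interaction: the diet effect should differ according to the microbiota the mouse carries. If every mouse carries responder microbiota, that interaction has no data behind it. Fewer tumours on the RS diet would be expected whether the starch acts through bacterial fermentation or directly on the mouse.

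A second link is also missing. Without before-and-after samples, or donors from both arms, nothing in the mouse work shows that eating RS changed participants' microbiota in a way that matters for tumours.

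These two links would tie the mouse result to the human trial, and Section 8 says secondary results will inform a later one. Comparator stool is already planned, with three collections per participant and an anaerobic tube in each kit, so the gap looks like one of selection and not of supply.

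**Working it through.** **What the stated contrast can estimate.** The plan gives no figure for the mouse study to reproduce, so the first check is structural. Take a model with four terms: mean, mouse diet, donor microbiota, and diet by microbiota.

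- Cells named in Section 8 (responder microbiota, two diets): design rank 2 of 4. The diet effect in responder-colonised mice is estimable. The microbiota effect, the diet effect in any other microbiota, and the interaction are not.
- With one comparator class added on both diets: rank 4 of 4, all estimable.

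So the limit exists and more mice would not remove it. The one estimable term is, however, the one Aim 3 asks about, within responders' microbiota.

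**What comparators would cost.** The inputs here are assumptions, since the documents give none: M mice, D donors, equal allocation, mouse SD s = 1, donor SD t in the effect concerned, totals held fixed, donor as the unit. The example is M = 48, D = 4, t = 0, 0.5, 1.0.

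| Quantity | Variance | SE at t = 0, 0.5, 1.0 | Ratio to planned |
|---|---|---|---|
| Planned diet effect | t²/D + 4/M | 0.289, 0.382, 0.577 | 1 |
| Diet effect in post samples, baseline samples added | t²/D + 8/M | 0.408, 0.479, 0.645 | 1.41, 1.25, 1.12 |
| Diet effect in responders, half the donors non-responders | 2t²/D + 8/M | 0.408, 0.540, 0.816 | 1.41 throughout |
| Diet effect in responders' post samples, both changes | 2t²/D + 16/M | 0.577, 0.677, 0.913 | 2.00, 1.77, 1.58 |
| Responder minus non-responder difference in diet effect | 4t²/D + 16/M | 0.577, 0.764, 1.155 | 2.00 throughout |

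For example, at t = 0.5 the planned variance is 0.25/4 + 4/48 = 0.0625 + 0.0833 = 0.1458, so SE = 0.382. The last row is 4 × 0.1458 = 0.5833, so SE = 0.764.

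**What the responder comparison would buy.** With two donors per group there are 2 degrees of freedom and the t multiplier is 4.303.

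- t = 0.5: 0.764 × 4.303 = 3.3 s.
- t = 0: 0.577 × 4.303 = 2.5 s.
- A larger study, M = 96, D = 8, t = 0.5: planned SE = √(0.25/8 + 4/96) = 0.27; doubled, 0.54; multiplier 2.447; half-width 1.32 s.

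If the whole diet effect were 1 s in responders and 0 in non-responders, none of these intervals would be expected to tell 1 from 0.

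**What the comparators would mean.** Section 5 says the products "will be unblinded by the Human Nutrition Lab to investigators once study and data analysis has been completed". If donors are sorted on SCFA change without the arm code, the non-responders include control participants who never ate RS and RS participants who did not adhere. Their microbiota might ferment RS normally in a mouse, so the contrast would not isolate microbial metabolism even if it were precise.

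Pairing a responder's later sample with baseline is more precise. Averaged over diets its variance is t²/D + 4/M, the same as the planned contrast if donors vary equally in both effects. But donors picked for a large SCFA rise are subject to regression to the mean and to time effects, and without control-arm donors neither can be removed.

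**The case for a change.** The strongest case for a change is that a stated mechanistic prediction should have a contrast able to separate it from its alternative, even in exploratory work. No such contrast is written down, the samples would exist anyway, and the smallest remedy is one sentence limiting the conclusion or citing controls held elsewhere. Untransplanted mice on both diets would address microbial dependence more directly than non-responders would.

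The structural part of this stands: a positive diet effect in responder microbiota would not demonstrate the predicted mechanism. The contrast still carries some information on it. A null result in microbiota chosen for SCFA response would count somewhat against the prediction, and a positive one gives some support to the Section 1 question of whether RS can potentially affect tumour formation.

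The case for redesign is weaker. Responders only is a reasonable proof-of-concept enrichment, and any comparator takes mice from the Aim 3 estimate. Untransplanted controls or baseline samples may already be in the animal protocol. A human feasibility protocol need not list the control groups of an animal experiment governed elsewhere. The limiting sentence would alter no result, because the plan states an expectation and draws no conclusion from it.

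**Conclusion.** No change follows. As Section 8 is written, the mouse study can estimate the RS-diet effect in responders' microbiota, which serves Secondary Aim 3. By itself it cannot test dependence on microbial metabolism, or whether the human intervention altered the microbiota in a way that affects tumours. Neither is a listed aim, all secondary work is exploratory, and the feasibility endpoints do not depend on it.

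Adding donor groups is a debatable trade: an SE 1.12 to 2.00 times larger for the Aim 3 effect, in return for a responder contrast with a half-width of 2.5 to 3.3 s at donor SD 0 to 0.5 s (48 mice, 4 donors), or a paired contrast open to regression to the mean. These sizes rest on assumed numbers of mice and donors and an assumed donor SD; the structural finding does not.

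The difference between Section 8, which restricts donors to responders, and Sections 1 and 10, which do not, is a matter of detail that the animal protocol can settle. That protocol and Figure 2 were not available, so this reading covers the visible text only. Whoever reports the mouse results should describe a positive finding as a diet effect in responder microbiota unless comparators were in fact used.
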